4.9.3 Determination of Sample Size

The sample size is based on that the investigation is looking at performance of Epaderm Cream measured as Improved Moisturisation evaluated by the subject. The answers will be recoded as three categories strongly agree/agree/neither agree nor disagree/disagree/strongly disagree. The expected distribution of the answers is strongly agree/agree 40%, neither agree or disagree 50% and disagree/strongly disagree 10%. Assuming a power of 80% and using a Sign test a total of approximately 40 subjects is needed in each subgroup (infants, children and adults).

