4. INVESTIGATION PLAN AND PROCEDURES

4.1 *Overall Design*

This investigation is designed as a prospective, non-randomised, single arm clinical investigation. Data will be collected from approximately 120 evaluable subjects, divided into

Title: Epaderm01 CIP with Integrated Central Amendment 1

Page 8(21)

Investigation Code Epaderm01 Final Version Approval date 2018-12-10

Central Amendment 1 Approval date 2019-03-14

three groups of approximately 40 subjects; infants (0-36 months old), children (3-18 years old) and adults (>18 years old), with the following indications: eczema, psoriasis and other dry skin conditions. Each subject will be followed during 4 weeks treatment, with a visit at baseline (visit 1), at 2 weeks (visit 2) and at 4 weeks (visit 3) treatment. An evaluable subject is a subject with a baseline visit and at least one follow-up visit.

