4.9.2 Statistical Evaluation

The results from the investigation period will be presented with descriptive statistics by visit. For continuous variables mean, standard deviation, median, minimum and maximum will be presented and for categorical data number and percentage will be presented.

To evaluate change in skin hydration (Improved Moisturisation) evaluated by subject from baseline to 4 weeks (strongly agree/agree/neither agree nor disagree/disagree/strongly disagree) Sign test will be used. This will be made totally and for each of the three groups (infants, children and adults). This will be presented descriptively.

Change over time for continuous variables will be tested using Wilcoxon signed rank test and for ordered categorical and dichotomous variables signed rank test will be used.

All tests are two-sided with alpha 0.05.

All efficacy analyses will be performed for an ITT/Full analysis set and also for a per protocol population. The safety variables will be studied for the Safety population. All results will be presented totally and for the three groups (infants, children and adults).

Applicable data will be collated into summary tables and figures. Those summary tables and figures will be integrated into the body of the Clinical Investigation Report. Data listings will be prepared for all captured data. The listings will be incorporated into applicable appendices of the Clinical Investigation Report (CIR).

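### Section 4.9.3 claims 80% power with about 40 subjects per age group, but the exact two-sided Sign test has about 74% there; the plan does not name the version of the test

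*Combined protocol and SAP*

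**What the plan says.** Section 4.9.3 bases the sample size on the subject's answer to the Improved Moisturisation item, recoded to three categories. It gives the planning assumption as "The expected distribution of the answers is strongly agree/agree 40%, neither agree or disagree 50% and disagree/strongly disagree 10" per cent, and then the result: "Assuming a power of 80% and using a Sign test a total of approximately 40 subjects is needed in each subgroup".

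Section 4.9.2 specifies the analysis of that item from baseline to 4 weeks: "Sign test will be used. This will be made totally and for each of the three groups (infants, children and adults"), and adds that this is presented descriptively. It also says "All tests are two-sided with alpha 0.05". It does not say whether the Sign test is exact, mid-p or a normal approximation. Section 4.9.3 gives no sample-size formula and does not say how neutral answers enter it.

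Section 4.1 sets the target in evaluable subjects ("Data will be collected from approximately 120 evaluable subjects, divided into" three groups of about 40) and defines the term: "An evaluable subject is a subject with a baseline visit and at least one follow-up visit".

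**The concern.** A Sign test discards neutral answers. If half of the answers are expected to be neutral, 40 subjects yield 20 usable answers on average, but the actual number varies from sample to sample. The exact test is also discrete: its power moves up and down as the usable count changes by one, and 20 happens to be a favourable count. A figure of 80% at 40 subjects may therefore hold for one convenient count or one version of the test, and not for the exact test as it would be run.

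This is the only sample-size justification in the CIP, and it is made for each age group. If the exact test is used, the chance that a group misses significance under the plan's own assumptions is about 26%, where the stated figure implies 20%. Leaving the version open also means that it could be chosen after the data are seen, and in a group of this size the choice can decide the result.

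**Working it through.** **Inputs.** P(agree) = 0.4, P(neutral) = 0.5, P(disagree) = 0.1, n = 40 per group and target power 80% (section 4.9.3); two-sided alpha 0.05 (section 4.9.2). So P(non-neutral) = 0.4 + 0.1 = 0.5, and among non-neutral answers P(agree) = 0.4/0.5 = 0.8, against 0.5 under the null.

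**1. Reproducing the plan's figure.** Three standard routes come close to 40 and 80%.

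- Exact test with the non-neutral count held at its mean, 40 × 0.5 = 20. The critical value is 15 of 20, and P(X ≥ 15 | 20, 0.8) = 80.4%.
- Normal formula conditional on the count: m = (1.96 × 0.5 + 0.842 × √(0.8 × 0.2))² / 0.3² = 19.3, so N = 19.3/0.5 = 38.5.
- Unconditional normal formula, which already lets the count vary: N = (1.96 × √0.5 + 0.842 × √(0.5 − 0.3²))² / 0.3² = 41.2. At n = 40 it gives 78.8% power.

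**2. Exact test with a random count.** Let M be the number of non-neutral answers. M ~ Binomial(40, 0.5), with mean 20 and SD √(40 × 0.25) = 3.2. Then

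power = Σ P(M = m) × P(exact two-sided p ≤ 0.05 | m, 0.8).

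Conditional power at counts near 20:

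| M | critical value | power |
|---|---|---|
| 18 | 14 | 71.6% |
| 19 | 15 | 67.3% |
| 20 | 15 | 80.4% |
| 21 | 16 | 76.9% |
| 22 | 17 | 73.3% |
| 23 | 17 | 84.0% |

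M equals 20 with probability only 12.5%. Averaged over M, power at n = 40 is 74.2%; a simulation of 400,000 trials also gave 74.2%. Power is 79.6% at n = 45 and 80.5% at n = 46, so 46 is the smallest group size that reaches 80%.

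**3. Other versions, same random count, n = 40.** True size comes from the same sum with 0.5 in place of 0.8.

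| version | power | true two-sided size |
|---|---|---|
| exact | 74.2% | 3.0% |
| continuity-corrected normal | 72.5% | 2.7% |
| mid-p | 80.0% | 4.6% |
| uncorrected normal | 81.6% | 5.3% |

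**4. Source of the gap.** In the normal approximation, power is 81.7% with the count fixed at 20 and 78.8% with it random, a cost of about 3 points. For the exact test the drop is 80.4% − 74.2% = 6.2 points. The rest reflects the discreteness of the exact test and the favourable position of 20.

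**5. Where the choice matters.** With M = 19 and 14 agree answers, exact p = 2 × P(X ≥ 14) = 0.064. Mid-p subtracts P(X = 14) = 0.022 from that and gives about 0.041. The two fall on opposite sides of 0.05.

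**6. Week-4 answers.** The documents give no rate of missing week-4 answers. As an assumed example, 36 answers of 40 give 69.1% (exact) or 75.8% (mid-p).

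**7. Pooled test.** With 120 subjects, exact power is 99.8%.

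**The case against.** The plan says only Sign test, never exact. With the count left random, mid-p and the uncorrected normal version give 80.0% and 81.6% at 40, and standard formulas give N of about 39 to 42. Section 4.9.3 says approximately 40. No calculation error is shown, and a count fixed at 20 appears nowhere in the text. All of this stands. A reader might infer that the 80% is simply wrong, or that the sponsor ignored the randomness of the non-neutral count. The documents support neither: the shortfall depends on the version used, and the random count alone explains only part of it.

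The objection does not remove the point. The exact binomial is a common form of the Sign test, and its power is 74%. The uncorrected normal version gets its power at a true error above the stated 0.05. Of the four versions checked, only mid-p gives about 80% while holding alpha, and the plan does not name it.

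A reader might also cube the power and conclude that the chance of significance in all three groups is 0.742³ = 41%, against 0.8³ = 51%. The plan has no rule that all three must succeed. It also tests the pooled group, and it calls the presentation descriptive.

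On the week-4 gap, section 4.3 asks sites to collect as much information as possible when a visit is missed, so the loss may be small. The mismatch between the two definitions remains, and section 4.9 has no dropout allowance and no rule for a missing answer.

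**Conclusion.** The point holds in conditional form. If the Sign test is exact, power per age group at 40 is 74.2%, about 6 points below the stated 80%, and 46 subjects would be needed. Across the versions that the plan leaves open, power at 40 runs from 72.5% to 81.6%. These figures rest on the 40/50/10 split, two-sided alpha 0.05 and 40 week-4 answers in each group.

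The pooled analysis is not in question. The difference between the evaluable definition and the 4-week test is real and can only lower power, whichever version is used. Its size cannot be read from the documents; 36 answers is an illustration. The matter is a worthwhile clarification of the plan and not evidence that the trial is badly undersized.

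**What to change.** Before database lock:

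- In section 4.9.2, name the version of the Sign test.
- In section 4.9.3, restate the power as about 74% per age group for the exact test, or about 80% if mid-p is prespecified, and name the sample-size method.
- In section 4.9.3, state that the figure assumes 40 week-4 answers per group, since evaluable subjects may have only a week-2 visit.

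The cost is a few sentences. Either the stated power becomes less favourable, or the plan commits to mid-p. Choosing mid-p does not make up for missing week-4 answers. Restating the figure needs no extra enrolment; keeping 80% with the exact test would need 46 week-4 answers per group.

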4.10 Changes to the Clinical Investigation Plan

No change in the investigation procedure will be effected without the mutual agreement between the Principal Investigator and Mölnlycke.

An amendment to the CIP may require notification or approval from EC/IRB and, in many countries, also the CA before implementation. Local requirements must be followed.

Mölnlycke will distribute CIP amendments to the Principal Investigator who is responsible for the distribution of these documents to the EC/IRB and staff concerned at his/her site. The distribution of these documents to the CA will be handled according to local practice.

Title: Epaderm01 CIP with Integrated Central Amendment 1

Page 17(21)

Investigation Code Epaderm01 Final Version Approval date 2018-12-10

Central Amendment 1 Approval date 2019-03-14

5. STATEMENTS OF COMPLIANCE

5.1 Ethics

5.1.1 Ethics review

The final CIP, including the final version of the Subject Information and Consent Form, must be approved or given a favourable opinion in writing by an EC in accordance with local requirements before enrolment of any subject into the investigation.

The Principal Investigator is responsible for informing the EC of any amendment to the CIP in accordance with local requirements.

5.1.2 Ethical Conduct of the Investigation

The clinical investigation will be performed in accordance with the ethical principles that have their origin in the most recent version of the Declaration of Helsinki, and with applicable regulatory requirements.

5.1.3 Subject Information and Consent Form

The Principal Investigator will ensure that the subject/subject's legal representative is given full and adequate oral and written information about the nature, purpose, possible risks and benefits of the investigation. Subjects/subject's legal representative must also be notified that they are free to discontinue participation in the investigation at any time. The subject/subject's legal representative should be given the opportunity to ask questions and time for consideration. The subject/subject's legal representative signed informed consent must be obtained before conducting any procedure specifically for the investigation. The original must be filed by the Principal Investigator. A copy of the Patient Information including the signed Consent Form should be given to the subject.

A sample of the Patient Information and Consent Form is enclosed (appendix B). If modifications are made according to local requirements, the new version must be approved by Mölnlycke.

If subject's legal representative is a parent, both parents' signatures are required.

The ICF process should be reflected in the source documents.

5.2 Regulatory and standards

5.2.1 Standards and other

The most recent version of ISO 14155 will be followed in addition to national regulations.

5.2.2 Subject data protection and confidentiality

The written Subject Information explains that the data will be stored in a computer database, maintaining confidentiality in accordance with national data legislation and that authorised representatives of Mölnlycke and/or a CA and/or EC/IRB, require direct access to those parts of the hospital/practice records relevant to the investigation, including medical history, for verification of data. All data computerised by Mölnlycke will be identified by subject number only.

Title: Epaderm01 CIP with Integrated Central Amendment 1

Page 18(21)

Investigation Code	Epaderm01	Final Version	Approval date	2018-12-10
Central Amendment 1 Approval date 2019-03-14				

The clinical investigation will be conducted in accordance with EU General Data Protection Regulation 2016/679.

5.3 Subject Protection Procedures

5.3.1 Procedures in Case of Medical Emergency

The Principal Investigator is responsible for ensuring that procedures and expertise are available to cope with medical emergencies during the investigation.

5.3.2 Insurance

Mölnlycke has product liability insurance.

5.4 Use of Information and Publications

The investigation data will be used internally by Mölnlycke in accordance with its post-market surveillance activities. The data may be used by Mölnlycke without revealing the identity of the subject. It may be used in printed and digital (e.g. websites) forms for internal and external scientific, educational and promotional purposes, e.g. peer-reviewed journal articles, conference posters, conference presentations, brochures, training materials, etc.

5.5 Record Retention

The Sponsor will retain all investigation documents for 10 years after the device leaves the market. The site is required to keep the documentation in accordance with local regulation.

5.6 Public Domain Access to the Clinical Investigation

A description of this clinical investigation will be available on <http://www.ClinicalTrials.gov> together with the NHI website.

6. INVESTIGATION TIMETABLE AND TERMINATION

Investigation start: Anticipated Q1 2019
Inclusion completed: Anticipated Q3 2019
Last subject out: Anticipated Q3 2019
Data base lock: Anticipated Q3 2019
Investigation Report: Anticipated Q4 2019

Mölnlycke retains the right to suspend or terminate this investigation at any time. The investigation could be prematurely discontinued if the investigation site is unable to fulfil the inclusion period according to the Clinical Investigation Agreement.

7. LITERATURE REVIEW AND REFERENCES

To determine the scientific background for this clinical investigation as well as to assess risks/benefits of the device, a literature review was conducted. The literature listed below was evaluated before serving as background information.

1. Medical Device Directive MDD/93/42/EEC as amended.
2. Clinical Evaluation MEDDEV 2.7/1, Rev 4; Jun 2016.
3. Post Market Clinical Follow up Studies MEDDEV 2.12/2 Rev 2; Jan 2012.

Title: Epaderm01 CIP with Integrated Central Amendment 1

Page 19(21)

Investigation Code	Epaderm01	Final Version	Approval date	2018-12-10
Central Amendment 1 Approval date 2019-03-14				

4. Internal Report: Clinical Evaluation Report, Epaderm Cream with Glycerine (SLS free), PD-420529 Rev: 02

8. DEFINITIONS AND PROCEDURES FOR REPORTING OF ADVERSE DEVICE EFFECT, SERIOUS ADVERSE DEVICE EFFECT AND DEVICE DEFICIENCY

Definitions:

Device Deficiency (DD)

Inadequacy of a medical device with respect to its identity, quality, durability, reliability, safety or performance.

Note: Device Deficiencies include malfunctions, use errors, and inadequate labelling.

All Device Deficiencies that might have led to a Serious Adverse Device Effect shall be reported in accordance with Serious Adverse Event reporting procedures, as specified below.

Adverse Event (AE)

Any untoward medical occurrence, unintended disease or injury, or untoward clinical signs (including abnormal laboratory findings) in subjects, users or other persons, whether or not related to the investigational medical device

Note:

- This definition includes events related to the investigational medical device or the comparator.
- This definition includes events related to the procedures involved.
- For users or other persons, this definition is restricted to events related to investigational medical devices.

Adverse Device Effect (ADE)

Adverse Event related to the use of the investigational medical device and the hydration measuring device.

Note:

- This definition includes adverse events resulting from insufficient or inadequate instructions for use, deployment, implantation, or operation, or any malfunction of the investigational medical device.
- This definition includes any event resulting from use error or from intentional misuse of the investigational medical device.

Serious Adverse Event (SAE)

Adverse Event that:

- a) led to death,
- b) led to a serious deterioration in the health of the subject, that either resulted in
 - 1) a life-threatening illness or injury, or
 - 2) a permanent impairment of a body structure or a body function, or

Title: Epaderm01 CIP with Integrated Central Amendment 1

Page 20(21)

Investigation Code Epaderm01 Final Version Approval date 2018-12-10**Central Amendment 1 Approval date 2019-03-14**

- 3) in-patient hospitalisation or prolonged hospitalisation or,
- 4) medical or surgical intervention to prevent life-threatening illness or injury or permanent impairment to a body structure or a body function.
- c) led to foetal distress, foetal death or a congenital abnormality or birth defect.

Note: Planned hospitalisation for a pre-existing condition, or a procedure required by the CIP, without serious deterioration in health, is not considered a serious adverse event.

Serious Adverse Device Effect (SADE)

Adverse Device Effect that has resulted in any of the consequences characteristic of a Serious Adverse Event.

PROCEDURES FOR SAE AND/OR SADE REPORTING OR REPORTING OF DD THAT COULD HAVE LED TO A SADE

The investigator must inform Mölnlycke within 1 calendar day of awareness of the event. When a SAE/SADE has been entered into the eCRF by the investigator /authorised site staff, the eCRF system will automatically generate a report to:

[contact].

In case of problem with the eCRF, a paper based version of the SAE/SADE report form (available in the investigator Site File) shall be used and sent by email to:

[contact].

All SAEs/SADEs that occurs during the Clinical Investigation shall be reported, whether or not they are considered causally related to the investigational device.

Device Deficiencies that might have led to SADE if either a) suitable action had not been taken, b) if intervention had not been made, or c) if circumstances had been less fortunate must be reported as a SADE.

The investigator is responsible for informing the EC/IRB and/or the Competent Authority of the SAE/SADE as per local requirements.

PROCEDURES FOR DD REPORTING

All DD shall be reported to Mölnlycke as soon as possible, without unjustified delay. If the DD might have led to a SADE, the reporting requirements for SADE described above must be followed. DDs can be either subject related or non-subject related depending on if the investigational device was used by a subject or not. Separate forms are used for subject related and non-subject related DDs. When a subject related DD has been entered into the eCRF by the investigator /authorised site staff, the eCRF system will automatically generate a report to:

[contact]

Non-subject related DDs are reported using the paper based report form located in the Investigator Site File. The completed form shall be sent by email to

[contact]

Procedures for ADE reporting

All ADE shall be reported by the investigator to Mölnlycke as soon as possible without unjustified delay. When a ADE has been entered into the eCRF by the investigator /authorised site staff, the eCRF system will automatically generate a report to:

[contact]

Title: Epaderm01 CIP with Integrated Central Amendment 1

Page 21(21)

Investigation Code Epaderm01 Final Version Approval date 2018-12-10**Central Amendment 1 Approval date 2019-03-14**

Causality Assessment

The relationship between the use of the investigational device and the occurrence of each ADE/SADE shall be assessed by the investigator and the sponsor and classified as device related or not related to the device.

Title: Epaderm01 CIP with Integrated Central Amendment 1

Page 1(3)

Investigation Code Epaderm01

CIP Approval date 2018-12-10

Central Amendment 1 Approval date 2019-03-14

CLINICAL INVESTIGATION PLAN (CIP)

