Further investigation variables/data**Baseline procedure as specified in appendix C:**

1. Subject's age and sex
2. Relevant Medical History (skin condition, date of diagnosis past/current, ongoing medication)
 - a. Classification (eczema, psoriasis and other dry skin conditions)
 - b. Location (Please specify)
 - c. Duration (Weeks/Months/Years)
 - d. Severity of diagnosis/condition according to local definition (Mild/Moderate/Severe)
3. Type of Relevant Previous Treatment
 - a. Topical: which type of medication/treatment
 - b. Systemic: which type of medication/treatment
 - c. Phototherapy
4. Concomitant medication or treatment relevant for the investigation
5. Instructions on frequency of treatment with Epaderm Cream
6. Did the subject shower and put on a moisturiser in the morning before visit? Instruct the subject not to shower nor put on Epaderm Cream before the follow-up visits.
7. Is the subject experiencing a flare of his/her skin condition at present (Yes/No/Not applicable)
8. Subject evaluation of itching in relation to skin condition/diagnosis (VAS scale)

Follow- Up visit, Visit 2 procedure will be registered for all enrolled subjects as specified in appendix C:

1. New relevant medical event? If Yes, please specify
2. Did the subject shower and put on a moisturiser in the morning before visit? (Yes/No)
3. Is the subject experiencing a flare of his/her skin condition at present (Yes/No/Not applicable)
4. Subject evaluation of itching in relation to skin condition/diagnosis (VAS scale)
5. Changes of concomitant treatment relevant for the investigation
 - a. Topical: which type of medication/treatment
 - b. Systemic: which type of medication/treatment
 - c. Phototherapy

End of Investigation Visit/Visit 3 procedure will be registered for all enrolled subjects as specified in appendix C:

1. New relevant medical event? If Yes, please specify
2. Did the subject shower and put on a moisturiser in the morning before visit? (Yes/No)
3. Is the subject experiencing a flare of his/her skin condition at present (Yes/No/Not applicable)
4. Subject evaluation of itching in relation to skin condition/diagnosis (VAS scale)
5. Changes of concomitant treatment relevant for the investigation
 - a. Topical: which type of medication/treatment
 - b. Systemic: which type of medication/treatment
 - c. Phototherapy

Title: Epaderm01 CIP with Integrated Central Amendment 1

Page 14(21)

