4.7.4 Safety Measurements and Variables

Only events related to the use of the investigational device and events related to inadequacies of the investigational device and the non-invasive device measuring the skin hydration, will be recorded as safety issues i.e. Adverse Device Effect (ADE), Serious Adverse Device Effect (SADE) and Device Deficiencies (DD). The definition of ADE, SADE and DD and procedures for reporting SADE and DD that could have led to a SADE are presented in section 8 of this CIP. All ADE, SADE and DD must also be recorded in the appropriate section of the eCRF. It is of utmost importance that all staff involved in the clinical investigation are familiar with the content of section 8. It is the responsibility of the Principal Investigator to ensure this.

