4.7.5 Anticipated ADEs

Epaderm Cream has been on the market in its present formulation since 2012 with over 5.8 million sold items (PD-420529 Rev: 02). Epaderm Cream has a low risk and is formulated with well-established ingredients commonly used in topical formulations.

The following events have been identified in the Product Risk Management Record:

- 1 skin reaction registered as Adverse Event – Non-reportable.
- 7 cases of skin reaction (3), rash (3) or burning skin (1) were registered as Adverse Events – Non-reportable in the Mölnlycke Quality Management System during the period July 2015 to Oct 2017.

The conclusion of the Product Risk Management Record is as following: Residual risks are negligible/tolerable and will be managed through provision of information from a Health Care professional, information on the product package or patient information.

Individuals hypersensitive to any of the ingredients may experience skin irritation. Epaderm Cream should not be used if you have any known allergy or sensitivity to any of the ingredients.

The Investigational Device should be used according to instructions for use (appendix D).

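### Non-serious skin reactions could be undercounted, because recorded worsening has no required causality review and no place in the safety analysis

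*Combined protocol and SAP*

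**What the plan says.** **What is recorded as safety.** Section 4.7.4 begins its rule with "Only events related to the use of the investigational device and events related to inadequacies of the investigational device", extends it to the hydration meter, and says that these "will be recorded as safety issues i.e. Adverse Device Effect (ADE), Serious Adverse Device Effect (SADE) and Device Deficiencies (DD"). Section 8 defines an ADE as an "Adverse Event related to the use of the investigational medical device and the hydration measuring device".

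**What is assessed for causality.** The closing paragraph of Section 8 reads: "The relationship between the use of the investigational device and the occurrence of each ADE/SADE shall be assessed by the investigator and the sponsor". The two permitted outcomes are related and not related. Section 8 also requires every SAE to be reported whatever its cause. It has no such rule for non-serious adverse events.

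**What the known risks are.** Section 4.7.5 lists one earlier skin reaction and "7 cases of skin reaction (3), rash (3) or burning skin (1"), and warns of irritation in hypersensitive users.

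**What else is collected.** The schedule in Section 4.3.1 has flare, severity, itch VAS and ODS at baseline and at both follow-up visits, and new relevant medical events at the two follow-ups. The items in Section 4.7.3 include "Is the subject experiencing a flare of his/her skin condition at present (Yes/No/Not applicable") and "New relevant medical event? If Yes, please specify".

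**What is analysed.** Section 4.9.2 says: "The safety variables will be studied for the Safety population". The safety endpoint in Section 4.2.2 is the number of ADEs. The other scores receive by-visit descriptive statistics, tests of change over time, and listings.

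**The concern.** Relatedness is decided before an event enters the safety record, and the joint assessment by investigator and sponsor comes afterwards. If a site reads a rash or burning as the subject's own disease and does not enter it as an ADE, no rule in the plan sends it to causality review.

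That misreading is plausible here. The subjects have eczema, psoriasis or other dry skin, and the named risks are skin events. The trial has one arm, so no control group shows how often flares would occur anyway. Section 1 states that safety alone would not call for this investigation, and Section 4.7.5 describes the cream as low risk. Yet Section 2 makes confirmation of safety part of the objective. A low ADE count could then mean few reactions or few labelled reactions, and the planned safety tables would not help the reader tell which.

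**Working it through.** **1. The path of a non-serious skin event**

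- Entered as an ADE: it is recorded as a safety issue (4.7.4), assessed by investigator and sponsor (8), and counted in the endpoint (4.2.2).
- Read as a flare: it is recorded under the flare item or as a new relevant medical event (4.7.3). No text links either item to causality assessment, and neither is a safety variable under 4.7.4.
- Serious: it is reported whatever its cause (8). The gap is therefore confined to non-serious events.

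**2. Can a reaction look like the disease?** The plan does not say so; this is an inference. The reaction terms in 4.7.5 are skin reaction, rash, burning and irritation. Grade 4 of the ODS scale in 4.7.3 includes redness and eczematous changes. The overlap is plausible on the plan's own terms.

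**3. Does the planned analysis show worsening?** By-visit percentages would give flare frequency, and tests of change compare visits. Neither counts the subjects who got worse. In a group that mostly improves, a few worsening subjects can be hidden by the improvers. No worsening table is planned for the Safety population.

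**4. Size.** The plan states no ADE rate and no labelling probability, so there is no figure to reproduce. The following is illustration only. N = 120 is the planned number of evaluable subjects (4.1), used as a stand-in for the Safety population. The true reaction rate t and the share s of reactions labelled as ADEs are assumptions, with at most one reaction per subject and subjects independent.

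Expected count = N × t × s. Chance of recording none = (1 − t × s)^N.

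For t = 5% and s = 25%: 120 × 0.05 × 0.25 = 1.5, and (1 − 0.0125)^120 = 22.1%.

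| Share labelled | Expected, t = 5% | Chance of none, t = 5% | Expected, t = 2% | Chance of none, t = 2% |
|---|---|---|---|---|
| 100% | 6.0 | 0.2% | 2.4 | 8.9% |
| 75% | 4.5 | 1.0% | 1.8 | 16.3% |
| 50% | 3.0 | 4.8% | 1.2 | 29.9% |
| 25% | 1.5 | 22.1% | 0.6 | 54.8% |

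**5. What a zero count would support.** With no recorded ADE, the one-sided 95% upper bound is 1 − 0.05^(1/N): 2.5% for N = 120 and 7.2% for one age group of 40. If only half of reactions were labelled (assumption), dividing the bound by 0.5 gives true rates up to about 4.9% and 14.4%.

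**The case against.** The strongest reply is that the data are not out of sight. Under Section 4.8.3 sponsor staff can view entries at once and raise queries, post-entry checks are run, and SADE, ADE and DD are reconciled. Section 4.8.1 adds source data verification. ADEs are scheduled at both follow-up visits, and withdrawing subjects are asked about them (4.4.4). Nothing forbids a site from entering a flare as an ADE, and Section 4.9.2 promises listings of all captured data. All of this stands. A reader might infer that the investigator alone settles whether a rash is a device effect; the documents do not support that. They support only that no second assessment is required for an event not entered as an ADE.

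A reader might also infer that the sponsor's review can take events out of the ADE count but never add any. Section 8 does not say how disagreement is resolved, or that a finding of not related removes an event. Because not related is an allowed outcome, ADE in that paragraph could even mean a suspected event. The wording is ambiguous, and that is itself a reason to clarify it.

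Further, worsening is not evidence of a device effect. Flares and one-grade changes may be ordinary fluctuation, and without a control arm no table can separate the two. This is right, and it limits how the proposed table may be read.

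Finally, Appendices C and F were not available for this review and may hold further eCRF fields. The causality rule in the body of the plan would still cover only ADEs and SADEs.

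**Conclusion.** The point holds as a possible bias. Following the stated rules can lower the count of non-serious ADEs in a trial meant to confirm safety. A reader might go further and conclude that reactions are being undercounted. The documents do not show that: they contain no reaction rate, no rate of mislabelling, and no statement that reactions resemble flares. The size is unknown. The figures above show only how the count would respond to assumed rates of 2% and 5%, and at 2% the absolute loss is small.

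The conclusion rests on two things: the inference that the named risks overlap with signs of the treated conditions, and the body text being complete on causality. It does not extend to serious events, nor does it mean that worsening goes unreported, since it appears in descriptive results and listings. The change is worth making because the data are already collected and the cost is low.

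**What to change.** 1. **Section 8.** Require a recorded causality assessment by both the investigator and the sponsor for every new relevant medical event and every new flare. Report both assessments, and count an event as an ADE if either judges it related. Define a new flare in advance, for example No at baseline and Yes at visit 2 or 3, and state how subjects already in flare or marked not applicable at baseline are handled.

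2. **Section 4.9.2.** Add a Safety-population table, overall and by age group, of the number and percentage of subjects worse than baseline at visit 2 or 3. The criteria would be ODS up by at least 1 grade, severity up by at least 1 category, a new flare, or an itch VAS rise above a prespecified threshold. Cross-tabulate with ADE yes/no, show missing follow-up, and label the table descriptive because there is no control arm. Confirm that severity is collected at follow-up: the schedule in 4.3.1 includes it, but the visit 2 and 3 lists in 4.7.3 do not.

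3. **Sections 4.7.4 and 8.** Reconcile the recording of related events only with the reporting of all SAEs.

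The cost is one causality field on the eCRF, a small review burden, one extra table, and possibly a slightly higher ADE count.
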